8.4. Statistical Analyses

Statistical analyses of the pharmacokinetic parameter data will be the responsibility of the statistics and programming, PAREXEL, under the direct auspices of statistics and programming, GlaxoSmithKline.

Pharmacokinetic data will be presented in graphical and/or tabular form and will be summarized descriptively by sex, by flag for evaluable data, by flag for injection location, by Site and overall. All pharmacokinetic data will be stored in the Archives, GlaxoSmithKline Pharmaceuticals, R&D.

All the derived PK parameters will be listed and summarized by sex and overall. For each of these PK parameters, with the exception of tmax and ratios, the following descriptive summary statistics will be calculated for each treatment: n, arithmetic mean with associated 95% CI, standard deviation, median, minimum, maximum, geometric mean with associated 95% CI, standard deviation of logarithmically transformed data, and between-subject coefficient of variation (CVb(%)).

For tmax and all concentration ratios, no geometric mean, nor associated 95% CI or standard deviation of logarithmically transformed data will be provided.

A sex-based comparison will be made for all the evaluable blood plasma PK parameters and estimated ratio between female vs male and its associated 90% CI will be provided.

Log-transformed PK parameters (AUC($0-\infty$), AUC(0-last), AUC(0-Wk4)), AUC(0-Wk8), AUC(0-Wk12), Cmax and t¹/₂ in blood plasma) will be analyzed by analysis of covariance (ANCOVA). The analysis will consider sex as fixed effect with BMI as continuous covariate using the mixed linear models procedure within the SAS/STAT module of the SAS system (Version 9.4 or higher). For each log-transformed PK parameter, point estimate and its associated 90% CI will be constructed for the sex difference (females vs males), and the difference and its 90%CI will be exponentiated to obtain the ratio of geometric least-squares (GLS) means and its 90% CI on the original scale.

```
Examples of SAS codes:
Proc Mixed;
    class subjid sex;
    model logPKpar = sex bmi/ddfm=kr;
    lsmeans sex;
    estimate 'Females vs Males' Sex 1 -1 /cl alpha=0.1;
run;
```

Ratios will be calculated for each subject. Evaluable PK parameters and calculated ratios will be summarized by gender and/or overall for each matrix.

CAB concentration in each matrix from the oral lead-in phase may be compared with Weeks 4, 8, and 12 concentrations if data permit using the exploratory model below. Descriptive summary will be provided by sex, by flag for evaluable PK, by flag for injection location and/or overall.

```
Examples of SAS codes: if model converges
Proc Mixed; (only include Ctau from Day 29, Weeks 4, 8 and 12)
    class subjid sex visit;
    model log(Ctau) = sex bmi visit/ddfm=kr;
    random subjid;
    lsmeans sex;
    lsmeans visit;
    estimate 'Females vs Males' Sex 1 -1 /cl alpha=0.1;
    estimate 'IM vs oral' visit -1 0.3333 0.3333 0.3333/cl
alpha=0.1;
    estimate 'Week 4 vs week 12' visit 0 1 0 -1/cl alpha=0.1;
    estimate 'Week 8 vs week 12' visit 0 0 1 -1/cl alpha=0.1;
    run;
```

Data display specifications for derived PK parameter summaries and listings are given in Section 11.1.3 of this RAP.

8.5. Relationship between Plasma CAB PK Concentration and Time Matched CVF, CT, VT, RT and RF CAB PK Concentration

The relationship between the plasma CAB PK concentration and the time matched CVF, CT, VT, RT and/or RF CAB PK concentration will be assessed with plots and by the SAS Proc Corr procedure.

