The CAB population PK model has been updated with PK data from ÉCLAIR (an additional 94 males) and LATTE-2 (an additional 230 participants; 216 males and 14 females), significantly increasing the data in the population PK dataset. The absorption rate constant for the entire population following CAB LA for the new model was increased approximately 2-fold ($4.54 \times 10^{-4} \text{ hr}^{-1}$ to $9.19 \times 10^{-4} \text{ hr}^{-1}$; i.e., more rapid absorption) as compared to the previous model and resulted in higher peak to trough ratios than previously observed. Sex remains a significant covariate in the model affecting the absorption rate constant following LA administration (KA LA), reflecting slower absorption in females than in males. Additional data from HPTN077 will increase the data obtained from females in the model to improve understanding of the impact of sex on KA LA.

Simulations based on the updated population PK model have been conducted to evaluate several potential dosing regimens. Currently, the HPTN077 Cohort 2 regimen (CAB LA 600 mg IM at two time points 4 weeks apart and every 8 weeks (Q8W) thereafter) is planned for evaluation in long-term Phase 3 PrEP studies. CAB LA 600 mg IM is the largest CAB LA dose that can be administered by single injection (3mL of 200 mg/mL nanosuspension). For these reasons, a single 600 mg IM is the proposed dose for evaluation of plasma and tissue PK in this study. Simulated profiles following a single CAB LA 600 mg IM injection one week after discontinuation of the CAB 30 mg once daily oral lead-in to evaluate safety are shown for males and females separately (Figure 2, Figure 3). The profiles show the last oral dose, which are expected to achieve mean peak and trough concentrations of 7.5 $\mu\text{g/mL}$ and 4.2 $\mu\text{g/mL}$, respectively. Consistent with the impact of sex on absorption, males will achieve a higher C_{max} of ~3 $\mu\text{g/mL}$ than females, who will achieve a C_{max} of ~1.35 $\mu\text{g/mL}$. Plasma concentrations are expected to remain above 4x PA-IC₉₀ (0.664 $\mu\text{g/mL}$) for approximately 4 weeks and above PA-IC₉₀ (0.166 $\mu\text{g/mL}$) for approximately 8 weeks in 95% of males; greater variability in concentrations between 8 and 12 weeks post injection is expected in males. Plasma concentrations are expected to remain above the PA-IC₉₀ (0.166 $\mu\text{g/mL}$) in 95% of females throughout the 12-week tissue sampling period.

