8. PHARMACOKINETIC ANALYSES

The reconciliation of the PK Case Report Form (CRF) and SMS2000 data will be performed by, or under the direct auspices of, Clinical Pharmacology Sciences and Study Operations (CPSSO), GlaxoSmithKline.

The merge of PK concentration data, randomisation and CRF data will be performed by, or under the direct auspices of, Clinical Statistics (Programmer), GlaxoSmithKline.

Derivation of pharmacokinetic parameters will be performed by, or under the direct auspices of, Clinical Pharmacokinetic Modelling Simulation (CPMS), GlaxoSmithKline.

Statistical analysis of pharmacokinetic parameters will be performed by, or under the direct auspices of, Clinical Statistics (Statistician), GlaxoSmithKline.

	Pharmacokinetic Concentration Data					
PC Windows Non- Linear (WNL) File	PC WNL file (CSV format) for the non compartmental analysis by Clinical Pharmacology Modelling and Simulation function will be created according to GSK PK guidance Note: Concentration values will be imputed as per GUI_51487					
Descriptive Summary Statistics, Graphical Displays and Listings	Refer to IDSL PK Display Standards. Refer to IDSL Statistical Principle 6.06.1. Note: Concentration values will be imputed as per GUI_51487 for descriptive summary statistics/analysis and summarized graphical displays only.					
Pharmacokinetic Para	ameter Derivation					
PK Parameter to be Derived by Programmer	The following PK parameters will be derived or extracted from SDTM PC file or SDTM PP by the Programmer: From SDTM PC Concentrations: Ctau on Day 29, C48h, C8d, CWk4, CWk8, CWk12, CWk24, CWk36, and CWk52 from concentration data (as data permit) & the ratios: VT:blood plasma, CT:blood plasma, CVF:blood plasma, CT:CVF, VT:CVF in women, and RT:blood plasma, RF:blood plasma and RT:RF in men and women (as data permit) at matched timepoints evaluated. From SDTM PP file: VT:blood plasma, CT:blood plasma, CVF:blood plasma, CT:CVF, VT:CVF in women, and RT:blood plasma, RF:blood plasma and RT:RF in men and women ratios for Cmax, AUC(0- ∞), AUC(0-last), AUC(0-Wk4), AUC(0-Wk8) and AUC(0-Wk12)					
Pharmacokinetic Para	ameter Data					
Is NQ impacted PK Parameters Rule Being Followed	Yes, refer to Standards for the Transfer and Reporting of PK Data using HARP.					
Descriptive Summary Statistics, Graphical Displays and Listings	Refer to IDSL PK Display Standards & refer to Standards for the Transfer and Reporting of PK Data using HARP.					

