3.4	Evaluable PK Plasma Parameter Summary	GSK1265744/LAI114433, Table 11.7	Summary of Result of Plasma Cabotegravir PK Parameter Comparisons Between Gender for Evaluable PK	Limited to evaluable PK data, and include sex and BMI in model, evaluate the difference between gender for AUC(0-t), AUC(0-∞), Cmax, AUC(0- Wk4), AUC(0-Wk8), AUC(0-Wk12) and t1/2,	3	SAC
3.5	Evaluable PK Plasma Parameter Summary	GSK1265744/LAI114433, Table 11.7	Summary of Result of Plasma Cabotegravir PK Parameter Ctau Comparisons Between Oral and IM for Evaluable PK	Limited to evaluable PK data, and include sex, BMI and Visits in model, evaluate the difference between IM vs oral CAB Ctau	3	SAC
3.6	Evaluable Tissue_fluid and PK Parameter(IM)	GSK1265744/LAI114433 Table 11.10	Summary of Tissue and Fluid Cabotegravir Parameters for each Treatment and Matrix by Site, by Evaluable Flag and by Gender	Include the CAB Parameters from tissue/fluid on Day 29 of oral lead-in, put each by variable on different page or sub-category	2	SAC
3.7	Tissue fluid Parameter	GSK1265744/LAI114433 Table 11.8	Listing of Derived Tissue and Fluid Cabotegravir Parameters	Sort by clinical site, sex and subject ID and flags for evaluable and injection locations	1	SAC

Table No.	Population	IDSL No. / Example Shell	Title	Programming Notes	QC Level	Deliverable Priority
3.8	Evaluable Tissue_fluid and PK Parameter (IM)	GSK1265744/LAI114433 Table 11.10	Summary of Tissue and Fluid to Blood Plasma Cabotegravir PK Parameter Ratio for each Matrix by Site and by Gender	Ratios of Tissue or fluid vs plasma for AUC(0-t), AUC(0-∞), Cmax, AUC(0- Wk4), AUC(0-Wk8), AUC(0-Wk12), for VT:blood plasma, CT:blood plasma, CVF:blood plasma, by site, by gender and overall	2	SAC
3.9	Evaluable Tissue_fluid and PK Parameter (IM)	GSK1265744/LAI114433 Table 11.10	Summary of Tissue and Fluid to Blood Plasma Cabotegravir PK Concentration Ratios of Each Visit by Site and by Gender	Ratios of Tissue fluid vs plasma for oral C29d, and IM C3d, C8d, CWk4, CWk8, CWk12 of VT:blood plasma, CT:blood plasma, CVF:blood plasma, by site, by gender and overall	2	SAC
3.10	Evaluable Tissue_fluid and PK Parameter(IM)	GSK1265744/LAI114433 Table 11.10	Summary of Tissue to Fluid Cabotegravir Parameter Ratios by Site and by Gender	Ratios of tissue vs fluid for AUC(0-t), AUC(0-∞), Cmax, AUC(0-Wk4), AUC(0- Wk8), AUC(0-Wk12), by site and by gender plus overall for ratios: CT:CVF, VT:CVF in women, and RT:RF in men and women (as data permit)	2	SAC

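### The exploratory Ctau model has no sex-by-visit term, so its single female:male ratio is a visit average that describes no individual visit

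*SAP*

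**What the plan says.** SAP 8.4 states that the oral lead-in concentration "may be compared with Weeks 4, 8, and 12 concentrations if data permit using the exploratory model below". The example code fits "model log(Ctau) = sex bmi visit/ddfm=kr" with a random subject intercept to Day 29 and Weeks 4, 8 and 12. It then requests "estimate 'Females vs Males' Sex 1 -1 /cl alpha=0.1", an IM versus oral contrast, and Week 4 and Week 8 each against Week 12. The code is marked as an example, to be used if the model converges. The programming note for Table 3.5 (SAP 11.1.3) reads "include sex, BMI and Visits in model, evaluate the difference between IM vs oral CAB Ctau".

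On the sex comparison in general, SAP 8.4 promises: "A sex-based comparison will be made for all the evaluable blood plasma PK parameters". The ANCOVA that follows (sex and BMI) covers the AUCs, Cmax and half-life, as does Table 3.4. The table in SAP section 8 also names Day 29 Ctau, CWk4, CWk8 and CWk12 as derived parameters, but neither the ANCOVA list nor Table 3.4 includes them.

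Protocol 4.5 describes sex as a covariate "affecting the absorption rate constant following LA administration (KA LA), reflecting slower absorption in females than in males". It predicts a Cmax of about 3 µg/mL in men and 1.35 µg/mL in women, and gives one oral peak and trough (7.5 and 4.2 µg/mL) for both.

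**The concern.** With main effects only, the expected log difference between women and men at equal BMI is the same constant at all four visits, and both sexes share one decline. A random subject intercept cannot absorb a sex difference that changes with visit. The protocol's mechanism says that it will change. Day 29 follows oral dosing, where the injection absorption rate plays no part. After the injection, slower absorption gives women a lower peak and a flatter decline, so F:M starts low and climbs.

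At stake is how Table 3.5 is read. A pooled F:M near 1 can look like no sex difference when early and late departures offset each other. The Week 4 and Week 8 versus Week 12 contrasts average two different declines. No planned output gives a modelled F:M with a CI at Weeks 4, 8 and 12.

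**Working it through.** The plan states no figure to reproduce. The check shows what the protocol's absorption model implies for F:M at the modelled visits.

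**Inputs from Protocol 4.5.** Oral peak 7.5 and trough 4.2 µg/mL; Cmax F:M = 1.35/3 = 0.45; population absorption rate 9.19e-4/h (4.54e-4/h in the previous population model). **From Protocol 9.2.1:** 8 women and 8 men.

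**Assumptions.** One compartment with first-order absorption. ke = ln(7.5/4.2)/24 = 0.0242/h. Male ka of 9.19e-4, 1.149e-3 or 1.370e-3/h, because no sex-specific value is given. Female ka is solved so that Cmax F:M = 0.45.

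**Formula.** C(t) = A·ka/(ke − ka)·[exp(−ka·t) − exp(−ke·t)]. By Week 4 the ke term is negligible, and 8 weeks is 1344 h, so

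F:M(Week 12) / F:M(Week 4) = exp[(kaM − kaF)·1344].

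This exceeds 1 whenever women absorb more slowly. For the first row below: exp[(9.19e-4 − 3.89e-4)·1344] = exp(0.712) = 2.04.

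**Results with equal F/CL** (F:M = 1 on Day 29; pooled = geometric mean over four visits):

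| Male ka | Female ka | Wk 4 | Wk 8 | Wk 12 | Wk 12 / Wk 4 | Pooled |
|---|---|---|---|---|---|---|
| 9.19e-4 | 3.89e-4 | 0.59 | 0.84 | 1.20 | 2.04 | 0.88 |
| 1.149e-3 | 4.81e-4 | 0.64 | 1.00 | 1.56 | 2.45 | 1.00 |
| 1.370e-3 | 5.68e-4 | 0.69 | 1.18 | 2.02 | 2.94 | 1.13 |

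Pooled, first row: (1 × 0.59 × 0.84 × 1.20)^(1/4) = 0.88.

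**Sensitivity.**
- Female F/CL at 0.7, 0.8, 1.0, 1.25 or 1.4 times male, with female ka re-solved and Day 29 F:M set to that multiple (15 combinations): change 1.6- to 3.7-fold, Week 12 F:M 0.86 to 2.77, pooled 0.69 to 1.43. Week 12 F:M exceeds 1 in 13 of the 15.
- Male ka 4.54e-4, equal F/CL: 0.51, 0.61, 0.72 at Weeks 4, 8 and 12. F:M rises 1.4-fold but does not reach 1.
- Male ka 2.5e-3, equal F/CL: 1.02, 2.81, 7.75. All three weeks are above 1.

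**Declines.** The fall from Week 4 to Week 12 is exp(ka·1344): 3.44-fold in men and 1.69-fold in women in the first row, 6.30 and 2.15 in the third. The pooled contrast returns the geometric mean: √(3.44 × 1.69) = 2.41 and √(6.30 × 2.15) = 3.68.

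**Pooled CI.** Assume between-subject log SD 0.5 and residual 0.4, total √(0.25 + 0.16) = 0.64. SE = √[(0.25 + 0.16/4)·2/8] = 0.269. With t(0.95, 13 df) = 1.771 the 90% CI is ×/÷ exp(0.477) = 1.61. It contains 1 in about 86-90% of trials with equal F/CL, and in about 62-90% over the 15 combinations.

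**Per-visit CI.** Half-width on the log scale is 1.771·SD·√(2/8): ×/÷1.76 at SD 0.64. The protocol's only between-subject CV, 139% from a small cohort on another regimen, gives SD = √ln(1 + 1.39²) = 1.04 and ×/÷2.5.

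**What the planned ANCOVA already shows.** In this model terminal half-life is ln 2/ka, so half-life F:M = kaM/kaF = 9.19e-4/3.89e-4 = 2.36, and 2.41 in the third row. F:M for AUC to Weeks 4, 8 and 12 is 0.49, 0.57, 0.64 in the first row and 0.52, 0.63, 0.72 in the third.

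**The case against.** The strongest reply is that this is an optional, exploratory example model whose table exists to compare IM with oral dosing; sex and BMI are adjusters, and main effects are a defensible economy with 8 per sex. That stands as a limit on impact. With complete, balanced data the IM versus oral contrast remains interpretable as a sex average, though it would shift if visits were missing unevenly by sex.

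A second reply also stands in large part: the planned ANCOVA gives modelled F:M for half-life, Cmax and interval AUCs, and by-sex geometric means and plots are planned. A reader might infer that the plan ignores a sex effect that varies over time. It does not; only the modelled F:M at the individual weeks is missing.

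A reader might also infer that the pooled CI is invalid because it often misses a single visit's ratio. That scores it against a target it does not estimate: for balanced data it is a proper interval for the visit-averaged log ratio. The fault lies in the label and in the usefulness of the average.

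Finally, one might take the protocol's statement that 95% of women stay above the PA-IC90 for 12 weeks, against about 8 weeks in men, as proof that F:M crosses 1. It is not: the protocol also expects greater male variability between Weeks 8 and 12, which lowers the male 5th percentile without moving the centre.

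**Conclusion.** The point holds as a minor one, worth considering. The model forces one F:M across visits over which the protocol's own mechanism makes it change. The upward direction from Week 4 to Week 12 needs only slower female absorption. The size (2.0- to 2.9-fold with equal F/CL, 1.6- to 3.7-fold otherwise) is illustrative: it rests on a simple absorption model and assumed male rates. A crossing of 1 is plausible but depends on F/CL and male ka. That the pooled CI usually contains 1 likewise depends on F/CL and on the assumed SD. Primary endpoints and the main purpose of Table 3.5 are unaffected.

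**What to change.** 1. Run the existing sex and BMI ANCOVA of SAP 8.4 separately on plasma Day 29 Ctau, CWk4, CWk8 and CWk12, and add F:M with 90% CI to Table 3.4. This delivers the promised comparison of all evaluable plasma parameters. Specify it in advance, with no switch triggered by the observed variances.
2. In Table 3.5, delete the pooled sex line or label it a visit average, label the week contrasts as sex-averaged, and keep IM versus oral.

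A sex-by-visit term may be added as support, but not as the lead analysis. In simulation (40,000 trials, 8 + 8 complete, male SD rising from 0.64 to 1.04 by Week 12, one way of representing the variability the protocol expects), its common-variance 90% CI covered the Week 12 F:M in only about 84% of trials; by-visit analysis kept about 90%. Confine all this to plasma, which is what Table 3.5 covers.

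Cost: a few table rows and example code, no new data. Per-visit CIs will be wide with 8 per sex (about ×/÷1.76 at log SD 0.64, ×/÷2.5 at 1.04), so they should be read as description.

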10. ABBREVIATIONS & TRADE MARKS

10.1. Abbreviations

Abbreviation	Description
ADaM	Analysis Data Model
AE	Adverse Event
ALT	alanine aminotransferase (SGPT)
ANCOVA	Analysis of Covariance
AST	Aspartate aminotransferase (SGOT)
ATC	Anatomical Therapeutic Chemical Classification level
AUC(0-last)	Area under the concentration time curve from time zero to last quantifiable time point
AUC(0-∞)	Area under the concentration time curve from time zero to infinity
AUC(0-Wk4)	Area under the concentration time curve from time zero to Week 4
AUC(0-Wk8)	Area under the concentration time curve from time zero to Week 8
AUC(0-Wk12)	Area under the concentration time curve from time zero to Week 12
BMI	Body mass index
BP	Blood pressure
BPM	Beats per minute
BQL	Below the quantification limit
CAB	Cabotegravir
CDISC	Clinical Data Interchange Standards Consortium
CI	Confidence interval
Cmax	Maximum observed concentration
CPK	Creatine phosphokinase
CPMS	Clinical Pharmacokinetic Modelling Simulation
CPSSO	Clinical Pharmacology Sciences and Study Operations
Οτ Οτ	Steady-state pre-dose CAB concentration
CT	Cervical tissue
CV	Coefficient of variance
CVb	Coefficient of variation between subjects
CVF	Cervicovaginal fluid
C48h	Concentrations observed at Day 3 (48h)
Cd8	Concentration observed at Day 8
CWk4	Concentration observed at Week 4
CWk8	Concentration observed at Week 8
CWk12	Concentration observed at Week 12
ECG	Electrocardiogram
GLS	Geometric least-squares
GSK	GlaxoSmithKline
HIV	Human immunodeficiency virus
IDSL	GSK's Integrated Data Standards Library
IM	Intramuscular(ly)
IP	Investigational product
ISR	Injection site reaction
	กฎธิธิการแต่ เป็นปีเป็น

Abbreviation	Description
LA	Long-acting
MRI	Magnetic resonance imaging
PK	Pharmacokinetic(s)
QTcB	QT duration corrected for heart rate by Bazett's formula
QTcF	QT duration corrected for heart rate by Fridericia's formula
RAP	Reporting and Analysis Plan
RF	Rectal fluid
RT	Rectal tissue
SAE	Serious adverse event(s)
SAS	Statistical Analysis Software
SD	Standard deviation
SDTM	Study Data Tabulation Model
SOP	Standard operating procedure
t1/2	Apparent terminal phase half-life
VT	Vaginal tissue

10.2. Trademarks

Trademarks of ViiV Healthcare

None

Trademarks not owned by ViiV Healthcare

PAREXEL SAS

Winonlin

201767

11. ATTACHMENTS

11.1. Table of Contents for Data Display Specifications

Listed below are the planned figures, tables and listings to be produced for inclusion in the clinical study report. Example shells from GSK1265744 studies LAI116815\final_cdisc, LAI114433\final, mid201741\final and GSK2881078\mid200030\final are located under the same compound (GSK1265744) in HARP. Example shells for some of the PK figures are also under the GSK2881078/mid200030 study reporting effort final.

Reporting Area

HARP Server	: US1SALX00259
HARP Area	: \ARPROD\GSK1265744\MID201767\Final_01
QC Spreadsheet	: \ARWORK\ GSK1265744\MID201767\Final\Documents

11.1.1. Study Population

Table No.	Population	IDSL No. / Example Shell	Title	Additional Programming Notes	QC Level	Deliverable Priority
1.1	Safety	LAI116815, Table 1.1	Summary of Analysis Populations	By Site and Treatment and Overall	3	SAC
1.2	Safety	LAI116815, Table 1.2	Summary of End of Study Record by Site and Overall	By Site and overall	2	SAC
1.3	Safety	LAI116815, Table 1.3	Listing of End of Study Record	Include the sub-reason where it has.	1	SAC
1.4	Safety	IDSL, IE4	Listing of Subjects with Inclusion/Exclusion Criteria Deviations		1	SAC
1.5	Safety	LAI116815, Table 1.4	Summary of Demographic Characteristics for Safety Population by Site	By Site and overall	2	SAC
1.6	Safety	IDSL, DM6	Summary of Race for Safety Population	By Site and overall	2	SAC
1.7	Safety	IDSL, CP_CM4	Summary of Concomitant Medications	Replace this listing with summary table by treatment if it has more than 4 pages of conmed data	1	SAC
1.8	Safety	IDSL, GN9	Listing of Genetics Subject Accountability	With Site information	1	SAC
1.9	Safety	LAI116815, Table 1.8	Listing of Treatment Non-Compliance by Site	Only list subjects with treatment non- compliance	1	SAC
1.10	Safety	LAI116815, Table 1.9	Summary of Protocol Deviations	Sorted by Site	1	SAC
1.11	All Screened	mid201741, Table 1.11	Summary of Screen Failure by Site	By Site	2	SAC

11.1.2. Safety

Figures

Figure No. 2.X	Population	IDSL No. / Example Shell	Title	Additional Programming Notes	QC Level	Deliverable Priority
1	Safety	LAI116815, Figure 2.3	Individual Subject ISR Duration for the Top 3 ISRs	Select the top 3 ISRs, like Pain, nodule, and induration	1	SAC

Tables

Table No.	Population	IDSL No. / Example Shell	Title	Programming Notes	QC Level	Deliverable Priority
2.1	Safety	LAI116815/Table 2.1	Summary of Exposure Data	Include number of dose(s), formulation/route, and injection site, needle length, fat depth, injection length, etc Sorted by Site	1	SAC
2.2	Safety	IDSL, AE2	Relationship of Adverse Event System Organ Classes, Preferred Terms, and Verbatim Text		2	SAC
2.3	Safety	IDSL, CP_AE1x	Summary of All Adverse Events	By Site and Overall	2	SAC
2.4	Safety	IDSL, CP_AE1x	Summary of Drug-Related Adverse Events	Include all study treatment related, not procedure related AEs By Site and Overall	2	SAC

Table No.	Population	IDSL No. / Example Shell	Title	Programming Notes	QC Level	Deliverable Priority
2.5	Safety	IDSL, CP_AE9a	Listing of Subjects with Serious Adverse Events		1	SAC
2.6	Safety	IDSL, CP_AE9	Listing of Adverse Events Leading to Permanent Discontinuation of Study Drug or Withdrawal from Study		1	SAC
2.7	Safety	LAI116815, Table 2.7	Listing of Grade 3 and 4 Adverse Events		1	SAC
2.8	Safety	LAI116815, Table 2.8	Summary of Injection Site Reaction by Site and Overall	This table summarizes the data at Subject level; 'LM CAB 600mg SD' only, by site and overall	2	SAC
2.9	Safety	LAI116815, Table 2.9	Summary of ISR Event by Toxicity Grade for Each Site and Overall	This table summarizes the data at event level for 'IM CAB 600mg SD' only; by site and overall	2	SAC
2.10	Safety	LAI116815, Table 2.10	Summary of Injection Site Reaction Symptoms Maximum Size Measured in Diameter(cm) by Site and Overall	Average the max of each event size for each subject with ISR by treatment; 'IM CAB 600mg SD' only	2	SAC
2.11	Safety	LAI116815, Table 2.11	Summary of Duration of Injection Site Reaction by Site and Overall	This table summarizes the data at ISR event level; IM CAB 600mg SD' only	2	SAC
2.12	Safety	LAI116815, Table 2.12	Listing of Grade 2 or Higher Injection Site Reaction Symptoms or ISR persist beyond 30 days	For ISR	2	SAC
2.13	Safety	LAI116815, Table 2.13 IDSL, LB13	Listing of Reference Ranges for Clinical Laboratory Tests		1	SAC
2.14	Safety	LAI116815, Table 2.14	Summary of Hematology Data by Treatment and Time by Site and Overall	Include oral CAB 30mg and 600mg LA in one table	2	SAC
2.15	Safety	LAI116815, Table 2.15	Summary of Change from Baseline in Hematology Data by Treatment and Time by Site and Overall		2	SAC

Table No.	Population	IDSL No. / Example Shell	Title	Programming Notes	QC Level	Deliverable Priority
2.16	Safety	LAI116815, Table 2.16	Summary of Clinical Chemistry Data by Treatment and Time for Each Site and Overall		2	SAC
2.17	Safety	LAI116815, Table 2.17	Summary of Change from Baseline in Clinical Chemistry Data by Treatment and Time for Each Site and Overall		2	
2.18	Safety	LAI116815, Table 2.19	Summary of Treatment Emergent Grade 2 or Higher Lab Abnormalities for Each Site and Overall	Include all tests in which we have DAIDS criteria.	1	SAC
2.19	Safety	LAI116815, Table 2.20	Listing of Treatment Emergent Grade 2 or Higher Lab Abnormalities	Include all tests in which we have DAIDS criteria.	1	SAC
2.20	Safety	LAI116815, Table 2.21	Summary of Vital Signs by Treatment and Time	Include BP, HR, and Temperature	2	SAC
2.21	Safety	LAI116815, Table 2.22	Summary of Change from baseline in Vital Signs by Treatment and Time	Include BP, HR, and Temperature	2	SAC
2.22	Safety	LAI116815, Table 2.23	Listing of All Vital Signs for Subjects with Any Values of Potential Clinical Importance		1	SAC
2.23	Safety	LAI116815, Table 2.24	Summary of ECG Findings		2	SAC
2.24	Safety	LAI116815, Table 2.25	Summary of ECG Values		2	SAC
2.25	Safety	LAI116815, Table 2.26	Summary of Change from baseline for ECG Values		2	SAC
2.26	Safety	LAI116815, Table 2.27	Summary of Category of QTc Data by Treatment and Time		2	SAC
2.27	Safety	LAI116815, Table 2.28	Summary of Category of QTc Change from Baseline by Treatment and Time		2	SAC
2.28	Safety	IDSL, CP_EG6	Listing of Clinically Significant ECG Abnormalities	List all data for a subject with clinically significant abnormalities	1	SAC
2.29	Safety	IDSL, CP_EG4, LAI116815, Table 2.29	Listing of All ECG Values for Subjects with Any Value of Potential Clinical Importance		1	SAC

Table No.	Population	IDSL No. / Example Shell	Title	Programming Notes	QC Level	Deliverable Priority
2.30	Safety	IDSL, SP1	Listing of Surgical Procedures	See format	1	SAC
2.31	Safety	IDSL, MH2	Listing of Medical Conditions	See format	1	SAC

